Safety and Efficacy of Trim II for Non- invasive Lipolysis and Circumference Reduction of Abdomen

NCT05398159

Last Updated Jun 3 2022

I N M O D E

Safety and Efficacy of Trim II for Non-invasive Lipolysis and Circumference Reduction of Abdomen.

Protocol No: DO609924A SIRB ID: 8659

Rev. Date: Jun 3 2022

Study Name: Safety and Efficacy of Trim II for Non-invasive Lipolysis and Circumference Reduction of Abdomen.

Protocol No.: DO609924A

Sponsor: InMode Ltd.
[name]
[name]
[name]
[contact]

I N M O D E

Safety and Efficacy of Trim II for Non-invasive Lipolysis and Circumference Reduction of Abdomen.

[figure not shown]
Protocol No: DO609924A SIRB ID: 8659

Rev. Date: Jun 3 2022

Approvals:

Revision Log:

Revision #	Date	Modification
A	January 2021	First Release
B	June 2022	

I N M O D E

Safety and Efficacy of Trim II for Non-invasive Lipolysis and Circumference Reduction of Abdomen.

Protocol No: DO609924A SIRB ID: 8659

Rev. Date: Jun 3 2022

1. Protocol Synopsis

Study Title	Safety and Efficacy of Trim II for Non-invasive Lipolysis and Circumference Reduction of Abdomen.
Protocol No	DO609924A
Sponsor	InMode Ltd.
Investigational Product	Trim II hands free device.
Study Design	Prospective, open label clinical study.
Principle Investigator and Study Site	Site 01: Site 02: Site 03: Site 04: Site 05:
Patient Population and Sample Size	At least 70 female and male subjects, from 5 investigational sites, aged 18-70 seeking non-invasive lipolysis and circumference reduction of abdomen will be enrolled.
Study Duration	Eligible subjects will receive 3 bi-weekly treatments (once in 2 weeks) with Trim II hands-free applicator belt according to the study protocol. Trim II hands-free applicator composed of 4 units applied to the abdominal area, using a single-use belt. Each treatment duration will be 45-60 minutes. Study duration for each subject is approximately 6 months (including screening, 3 treatments and 2 follow-up visits at 1 and 3 months post last treatment). Histological samples will be taken from treated area of 8-10 subjects (in total) at baseline and at 3 months follow-up visit. Overall study duration will be approximately 12 months, depending on the subject recruitment rate.

I N M O D E

Safety and Efficacy of Trim II for Non-invasive Lipolysis and Circumference Reduction of Abdomen.

Protocol No: DO609924A SIRB ID: 8659

Rev. Date: Jun 3 2022

Endpoints	
Primary Endpoints:
 
 • Efficacy of the Trim II treatment for lipolysis and abdominal circumference reduction. Evaluation of change in abdomen circumference using tape measurements in cm at the 3 months follow-up visit comparing to baseline. Success criteria: Statistically significant reduction in abdominal circumference tape measurements at the 3 months follow-up visit compared to baseline • Safety of the Trim II treatment for lipolysis and abdominal circumference reduction. The occurrence of adverse events will be followed throughout the whole study. Observation, assessment and recording of potential reactions by the investigator. Evaluations will be done immediately after each treatment and at the follow-up visits. The frequency, severity and causality of reactions will be recorded. 
Secondary Endpoints:
 
 • Efficacy of the Trim II treatment for fat and circumference reduction in abdomen, as assessed by two blinded evaluators. Evaluation of photographs at baseline and 3 months follow-up. Success criteria: Correct identification of baseline and 3-month follow-up visit photographs in at least 70% of treated subjects by two blinded evaluators. • Change in abdominal fat thickness measured by ultrasound imaging (USI) at the 3 months follow-up visit comparing to baseline. Success criteria: statistically significant change in fat thickness measurements at the 3 months follow-up visit compared to baseline. • Evaluation of change in histological samples at 3 months follow-up visit comparing to baseline. Success Criteria: Effect on fat tissue while the dermal and epidermal layers are intact with no adverse skin events • Subject's satisfaction with study treatment at 3 months follow-up visit. Subject's satisfaction with the therapy results evaluated through the Subject Satisfaction Questionnaire (5-point scale). • Treatment comfort during the study treatment. Subjects will be asked to rate discomfort using Subject's discomfort (pain) level after each treatment evaluated using the Therapy Comfort Questionnaire
Visits	
Each subject will undergo at least 5 study visits including: screening, 3 treatments and 2 follow-up visits. Duration of each treatment visit is approximately 2 hours.
 
Visit 1: Screening, baseline and 1st treatment (can occur on th same day)

I N M O D E

Safety and Efficacy of Trim II for Non-invasive Lipolysis and Circumference Reduction of Abdomen.

Protocol No: DO609924A SIRB ID: 8659

Rev. Date: Jun 3 2022

	
 - Screening will be performed to determine subject eligibility as well as to collect the required medical information and obtain signed Informed Consent - Baseline abdominal fat thickness measured by ultrasound - Baseline photographs of treatment area - Baseline weight and height (BMI calculation) - Baseline circumference tape measurement - Baseline caliper measurement - Baseline histologies (8 subjects) - Abdominal 1st treatment will be done using the TRIM II hands-free applicators belt according to IFU - Therapy Comfort Questionnaire 
* Treatment may occur on the same day of screening or within 3 weeks following screening.
 
Visits 2-3: 2nd, 3rd treatments – each 2 weeks following previous visit
 
 - Weight and height (BMI calculation) - Circumference tape measurement - Caliper measurement - Abdominal treatment will be done using the TRIM II hands-free applicators belt according to IFU - Therapy Comfort Questionnaire 
Visit 4: Follow-up visit – 1 month following last treatment
 
 - Treatment area will be photographed - Weight and height (BMI calculation) - Circumference tape measurement - Caliper measurement 
Visits 5: Follow-up visit – 3 months following last treatment
 
 - Treatment area will be photographed - Weight and height (BMI calculation) - Circumference tape measurement - Caliper measurement - Abdominal fat thickness measured by ultrasound - Histologies (8 subjects) - Subject's satisfaction 
After each treatment and at all visits, skin response and adverse events will be recorded.

Main Eligibility Criteria	
Inclusion Criteria
 
 - Female and male subjects, aged 18-70. - BMI ≤ 30. - Subjects seeking non-invasive lipolysis and circumference reduction of abdomen - Female should not be pregnant or lactating and must be either post-menopausal, surgically sterilized, or using a medically acceptable form of birth control at least 3

I N M O D E

Safety and Efficacy of Trim II for Non-invasive Lipolysis and Circumference Reduction of Abdomen.

Protocol No: DO609924A SIRB ID: 8659

Rev. Date: Jun 3 2022

months prior to enrolment (i.e., oral contraceptives, contraceptive implant, barrier methods with spermicide or abstinence).

- In addition, negative urine pregnancy test as tested before each treatment and at the last visit for women with childbearing potential (e.g. not menopause).
- General good health confirmed by medical history and skin examination of the treated area.
- The subjects should understand the information provided about the investigative nature of the treatment, possible benefits and side effects, and sign the Informed Consent Form, including permission to use photography.
- The subjects should be willing to comply with the study procedure and schedule, including the follow up visits, and will refrain from using any other abdominal treatment methods during the entire study period.

Exclusion Criteria

- Active electrical implant/device in any region of the body, including pacemaker or internal defibrillator
- Permanent implant in the treated area such as metal plates, screws or silicon, metal piercing or other.
- Current or history of skin cancer, or current condition of any other type of cancer, or pre-malignant moles.
- Severe concurrent conditions, such as cardiac disorders, sensory disturbances, epilepsy, uncontrolled hypertension, and liver or kidney diseases.
- History of skin disorders, keloids, abnormal wound healing, as well as very dry and fragile skin.
- History of bleeding coagulopathies or use of anticoagulants except for low-dose aspirin.
- Patients with history of diseases stimulated by heat, such as recurrent Herpes Simplex in the treatment area, may be treated only following a prophylactic regimen.
- Impaired immune system due to immunosuppressive diseases such as AIDS and HIV or use of immunosuppressive medications.
- Pregnancy and nursing.
- Poorly controlled endocrine disorders, such as Diabetes, or thyroid dysfunction and hormonal virilization.
- Isotretinoin (Accutane) within last 6 months.
- Any active condition in the treatment area, such as sores, Psoriasis, eczema, and rash, open lacerations, abrasions or lesions, infection in the area to be treated.
- Any surgical procedure in the treatment area within the last 12 months or before complete healing.
- Having received treatment with light, laser, RF, or other devices in the treated area within 2-3 weeks for non-ablative procedures, and 6-12 weeks for ablative fractional

I N M O D E

Safety and Efficacy of Trim II for Non-invasive Lipolysis and Circumference Reduction of Abdomen.

Protocol No: DO609924A SIRB ID: 8659

Rev. Date: Jun 3 2022

laser resurfacing (according to treatment severity) prior to treatment, except special recommendations.

- Use of non-steroidal anti-inflammatory drugs (NSAIDS, e.g., ibuprofen-containing agents) one week before and after each treatment session, as per the practitioner's discretion.
- As per the investigator's discretion, refrain from treating any condition which might make it unsafe for the patient.
- Participated in another investigational drug or device study or have completed the follow-up phase for any previous study less than 30 days prior to the first evaluation in this study.

Statement of Compliance

This study will be conducted in accordance with the Code of Federal Regulations on the Protection of Human Subjects (45 CFR Part 46), any other applicable US government research regulations, and institutional research policies and procedures. The Principal Investigator will assure that no deviation from, or changes to the protocol will take place without prior agreement from the sponsor and documented approval from the Institutional Review Board (IRB), except where necessary to eliminate an immediate hazard(s) to the trial participants.

I N M O D E

Safety and Efficacy of Trim II for Non-invasive Lipolysis and Circumference Reduction of Abdomen.

Protocol No: DO609924A SIRB ID: 8659

Rev. Date: Jun 3 2022

TABLE OF CONTENTS

1. PROTOCOL SYNOPSIS	4
2. INTRODUCTION & STUDY RATIONALE	12
3. DEFINITIONS, ACRONYMS AND ABBREVIATIONS.....	12
4. DEVICE DESCRIPTION	13
5. STUDY OBJECTIVES	14
6. STUDY ENDPOINTS.....	14
6.1 Primary Endpoints	14
6.2 Secondary Endpoints.....	15
7. STUDY POPULATION	15
7.1 General Considerations	15
7.2 Subject Withdrawal and Replacement	15
7.3 Subject Identification.....	16
7.4 Inclusion Criteria.....	16
7.5 Exclusion criteria.....	16
8. STUDY PROCEDURES.....	17
8.1 Visit 1: Screening, baseline and 1 st treatment	17
8.2 Visits 2-3: 2 nd , 3 rd treatments , every 2 weeks following previous visit	19
8.3 Visit 4: Follow-up visit – 1 month following last treatment	20
8.4 Visit 5: Follow-up visit – 3 months following last treatment	20
8.5 Table 1 – Clinical Evaluation Measurements and Tools	21
9. ADVERSE EVENTS REPORTING	21
9.1 Definitions	21
9.2 Anticipated Adverse Events in this Clinical Evaluation	22

I N M O D E

Safety and Efficacy of Trim II for Non-invasive Lipolysis and Circumference Reduction of Abdomen.

Protocol No: DO609924A SIRB ID: 8659

Rev. Date: Jun 3 2022

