6.2 Secondary Endpoints

- Efficacy of the Trim II treatment for fat and circumference reduction in abdomen, as assessed by two blinded evaluators. Evaluation of photographs at baseline and 3 months follow-up. Success criteria: Correct identification of baseline and 3-month follow-up visit photographs in at least 70% of treated subjects by two blinded evaluators.
- Change in abdominal fat thickness measured by ultrasound imaging (USI) at the 3 months follow-up visit comparing to baseline. Success criteria: statistically significant change in fat thickness measurements at the 3 months follow-up visit compared to baseline.
- Evaluation of change in histological samples at 3 months follow-up visit comparing to baseline. Success Criteria: Effect on fat tissue with no adverse effect in dermal tissue
- Subject's satisfaction with study treatment at 3 months follow-up visit. Subject's satisfaction with the therapy results evaluated through the Subject Satisfaction Questionnaire (5-point scale) as follows: +2 = Very satisfied; +1 = Satisfied; 0 = Indifferent; -1 = Disappointed; -2 = Very disappointed.
- Therapy comfort during the study treatment. Subjects will be asked to classify skin reactions (subjective evaluation) and will rate discomfort using visual analog pain scale from 0 (no pain) to 10 (intolerable pain) immediately after each treatment session.

7. Study Population

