8.4 Visit 5: Follow-up visit – 3 months following last treatment

- Treatment area will be photographed
- Pregnancy Urine Test prior to the treatment
- Weight and height (BMI calculation)
- Circumference tape measurement
- Caliper measurement
- Abdominal fat thickness measured by ultrasound
- Histologies (8 subjects)
- Subject's satisfaction

After each treatment and at all visits, any adverse events will be recorded.

	Safety and Efficacy of Trim II for Non-invasive Lipolysis and Circumference Reduction of Abdomen.	
	Protocol No: DO609924A SIRB ID: 8659	Rev. Date: Jun 3 2022

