14.1 Analysis Sets

- Safety Analysis Set

The safety analysis set will include all subjects using Embrace procedures at least a single time.

- Performance Analysis Set

Performance analysis set will consist of all subjects providing at least one post treatment performance measurement.

- Treatment of Missing Values

Only observed data will be used; i.e. missing data will not be imputed.

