Appendix 3.0: Photography

At each of the specified time points; photographs of the treated areas should be taken by investigator or their designee.

- Photographs should be taken in a private room or area of the clinic under controlled conditions, including the distance from the camera to the subject, height of the camera, background, camera positioning, subject's positioning and lighting in order to achieve high-quality before & after sets.
- Consistent lighting- Lighting should be preferably projected from about 45° angle in order to emphasize the treatment area appearance.
- For consistency purposes, the same person should ideally take all study photographs.
- The digital files should follow a consistent standard naming scheme containing subject initials and study ID #, visit or visit date.

Specific photography details:

Area: Abdomen:

Five photographs should be taken at each specified time point

- Front
- 45° from the right side
- 90° from the right side
- 45° from the left side
- 90° from the left side

The subject's arms should remain out of the way; it is best to either cross them over each other in front of the chest or hold them up at a 90° angle to the body, ensuring that they do not rest on the chest or touch the body and that they do not cast a shadow in the photograph.

	Safety and Efficacy of Trim II for Non-invasive Lipolysis and Circumference Reduction of Abdomen.	
	Protocol No: DO609924A SIRB ID: 8659	Rev. Date: Jun 3 2022

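### Baseline biopsies in the photographed area could reveal image order in 8 of at least 70 subjects, and the photograph endpoint does not report these subjects separately

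*Combined protocol and SAP*

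**What the plan says.** - **Biopsies.** The Study Duration row of the Protocol Synopsis reads "Histological samples will be taken from treated area of 8-10 subjects (in total) at baseline and at 3 months follow-up visit". The Visits row of the synopsis, sections 8.1 and 8.4, Table 1 in 8.5 and Appendix 1.0 all give 8 subjects. Table 1 places the biopsies in the treatment area.
- **Photographs.** The baseline list has "Baseline photographs of treatment area" and the 3-month list (8.4) has "Treatment area will be photographed". Photographs come before histology in both lists, but no text makes that order mandatory.
- **Photograph endpoint.** Section 6.2 sets the success criterion: "Correct identification of baseline and 3-month follow-up visit photographs in at least 70% of treated subjects by two blinded evaluators".
- **Photographic method.** Appendix 3.0 says "Five photographs should be taken at each specified time point" and asks for angled light "in order to emphasize the treatment area appearance". It standardises distance, background and posture. It has no step for covering, cropping or masking a biopsy site.
- **Analysis set.** Section 14.1 defines the performance set as "all subjects providing at least one post treatment performance measurement". Neither this set nor the endpoint text treats biopsied subjects separately.

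**The concern.** The evaluators' task is to say which image is later, so anything present in only one image is a cue. If the listed order is followed, the baseline image precedes the first biopsy and cannot show its mark. The 3-month image may show a healed one. An evaluator who notices it could order the pair correctly without seeing any change in fat or contour.

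The photograph reading is the only efficacy assessment described as blinded in an open-label study. Its success rule is a fixed 70% cut, so a few subjects could decide a close result, and that result would then be hard to attribute to treatment alone.

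**Working it through.** The plan gives no power calculation, null rate or test for this endpoint, so there is no figure to reproduce.

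**Inputs from the documents**
- Biopsied subjects: b = 8 (10 at the upper end of the synopsis range).
- Enrolment: at least 70 (Synopsis, 7.1), so n = 70 is the minimum.
- Bar: 0.70 × 70 = 49 correct.
- Visit windows: Appendix 1.0.

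**Assumptions, none of them in the documents**
- One correct/incorrect result per subject, all 70 evaluable, subjects independent.
- p = true identification rate without any biopsy cue.
- r = share of marks that give the order away.
- m = share of noticed marks that are misread.

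**1. Age of the mark at the 3-month photograph.** From a biopsy at screening/baseline, the minimum is 0 + 12 + 12 + 80 = 104 days and the maximum is 21 + 16 + 16 + 100 = 153 days.

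**2. Share of subjects.** 8/70 = 11.4%; 10/70 = 14.3%. Both are ceilings, because enrolment may exceed 70.

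**3. Shift in the expected rate.** A biopsied subject is correct with probability r + (1 − r)p, the others with p. The shift is (b/n) × r × (1 − p). At p = 0.60:
- 8 of 70: (8/70) × 0.40 × r = 1.1, 2.3, 4.6 points for r = 0.25, 0.5, 1.
- 10 of 70: 1.4, 2.9, 5.7 points.
- 8 of 90 (illustrative larger enrolment): 0.9, 1.8, 3.6 points.

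**4. Chance of reaching 49 of 70, 8 biopsied** (exact: Binomial(62, p) plus Binomial(8, r + (1 − r)p)):

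| True rate p | r = 0 | r = 0.25 | r = 0.5 | r = 1 |
|---|---|---|---|---|
| 50% (guessing) | 0.05% | 0.1% | 0.2% | 0.8% |
| 60% | 5.5% | 7.9% | 11.0% | 19.7% |
| 65% | 22.8% | 28.4% | 34.6% | 48.4% |
| 70% | 55.9% | 62.0% | 68.0% | 79.1% |
| 80% | 98.4% | 98.9% | 99.2% | 99.7% |

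With 10 biopsied and every mark revealing, guessing reaches the bar 1.4% of the time.

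**5. Misread marks.** With 8 biopsied, p = 0.60 and half the marks noticed, a biopsied subject is correct with probability q = 0.5(1 − m) + 0.5 × 0.60, and the shift is (8/70)(q − 0.60).
- m = 0: q = 0.80, shift +2.3 points, chance of success 11.0%.
- m = 0.25: q = 0.675, +0.9 points, 7.2%.
- m = 0.40: q = 0.60, no shift, 5.5%.
- m = 0.50: q = 0.55, −0.6 points, 4.5%.

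**6. Bar without the biopsied subjects.** 0.70 × 62 = 43.4, so 44 of 62 (71.0%). 0.70 × 60 = 42, so 42 of 60 (70.0%).
- At p = 0.80 the chance of success is 98.4% on 70, 96.9% on 62 and 97.8% on 60.
- If both bars must be met and no mark is revealing, the chance with 8 left out is Σₖ P(K = k) × P(X ≥ max(44, 49 − k)), with K ~ Binomial(8, 0.80) and X ~ Binomial(62, 0.80). This gives 96.7%. The same sum with 10 left out (42 of 60) gives 97.4%.
- At p = 0.70 the standard error √(0.7 × 0.3/n) goes from 5.5 points (n = 70) to 5.8 (62) or 5.9 (60). The chance of success goes from 55.9% to 49.6% on 62 or 56.3% on 60. Requiring both bars, it is 46.8% or 50.2%.

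**The case against.** The strongest reply is that the central premise is not in the documents. Nothing visible states the biopsy's type, size, position or closure, or whether a mark would be seen in abdominal views 104 to 153 days later. Both r and m are assumed, and step 5 shows that misreading can cancel or reverse the effect. This stands: the documents settle neither the size nor the direction.

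The reach is also small: one of several secondary endpoints, and 8 to 10 of at least 70 subjects. The largest figures need every mark to give the order away. This stands too and keeps the severity low.

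The plan states no rule for combining the two evaluators, so the success probabilities illustrate sensitivity under a one-result-per-subject assumption and do not evaluate the plan's own decision rule. That is fair.

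A further reply is that photographs are already listed before histology. That does not help, because the cue arises in exactly that order. With the order reversed at baseline, a fresh wound would be the cue.

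A reader might infer that the blinded reading is broken, or that the biopsies alone could carry the endpoint. The documents do not support either. No mark is shown to be visible, nothing says what evaluators know about the biopsies, and guessing stays below 1% with 8 biopsied even if every mark is revealing. The scar listed among risks in 9.2 and 13.1 is a device effect and is no evidence about biopsy marks.

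**Conclusion.** The point holds as a possible bias in one secondary endpoint. The plan as written lets a cue unrelated to fat into the photograph reading for up to about 11% of subjects (14% with 10), and no visible text masks the site or separates these subjects. Part of the protocol is redacted, but the photography appendix is readable and has no such step.

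At a true rate of 60%, the expected rate would rise by roughly 1 to 5 points with 8 biopsied, if marks are visible, noticed and read as later. The chance of success changes materially only for true rates near or somewhat below 70%. It hardly changes at 50% or 80%. The primary circumference endpoint is measured by tape and is unaffected. Severity is low; the reason to act is that the remedy costs little.

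**What to change.** **Recommended.** State in 6.2 and 14.1 that the photograph identification rate will be reported with and without the biopsied subjects, and that success is claimed only if the 70% bar is also met without them: 44/62 with 8 left out, 42/60 with 10, if 70 are evaluable. This needs no extra procedure. The price is a small loss of precision: at a true rate of 80%, the chance of success falls from 98.4% to 96.9% or 97.8% on the reduced set, or to 96.7% or 97.4% when both bars must be met. The cost is larger for a true rate right at the bar (step 6), partly because 44/62 rounds up to 71.0%.

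**Optional.** Mask the biopsy site at the same position in both images before they reach the evaluators. This shows that a subject was biopsied but not which image is later. It means editing up to 8 × 2 × 5 = 80 images (100 with 10 subjects). The site must be recorded at biopsy so that it can be found on the earlier baseline image, and the mask hides a little of the area being judged.

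Fixing the order of photographs and biopsy is reasonable but does not by itself remove the cue.
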